9.7. Cardiovascular Endpoints Interim Analyses

Each stage of the study uses a group sequential design with planned interim analyses as described below.

Stage 1

The first interim analysis will be conducted at the later of 1) the time at which a minimum of 130 adjudicated MACE plus events have accrued throughout the Phase 2 and Phase 3 development program or 2) the approximate time at which all necessary data are available to support the filing of ertugliflozin. The purpose of this interim analysis is to provide data for a meta-analysis of cardiovascular events that will support the initial regulatory submissions and rule out a hazard ratio of 1.8 (an 80% increase in cardiovascular risk relative to the non-ertugliflozin comparator group). If necessary (ie, if the first interim analysis is conducted with less than 173 MACE plus events and fails to rule out an HR>1.8), a subsequent final Stage 1 analysis will be conducted after at least 173 adjudicated MACE plus events have accrued. For each of these analyses, the two-sided adjusted CI for the HR will be calculated using an O’Brien-Fleming spending function to preserve the overall Type I

090177e187d04317\Approved\Approved On: 14-Mar-2016 14:12

error rate of 2.5% with respect to the non-inferiority margin of 1.8. The analysis at approximately 130 MACE plus events corresponds to an information fraction of approximately 75% with respect to the Stage 1 MACE plus analyses and the amount of alpha to be spent for this analysis is about 1.0% (one-sided). If at either of these looks, the upper bound of the two-sided adjusted CI is <1.8 , this result will be communicated to the E-DMC by an independent statistician(s) and may subsequently be submitted to regulatory authorities. If, on the other hand, the upper bound of the adjusted CI is >1.8 at both of these analyses, then the study may be stopped for futility.

Stage 2

Once the 1.8 threshold has been met, the study will continue to Stage 2. An interim analysis will take place when approximately 714 MACE events have accrued in this study. The purpose of this analysis will be to rule out an HR of 1.3 for MACE and to sequentially test for superiority on the secondary endpoints of cardiovascular death or hospitalization for heart failure (composite), cardiovascular death (individual component), and the renal composite. If necessary (ie, if the interim analysis fails to rule out an HR >1.3 or to achieve superiority on both of the secondary CV endpoints), the final analysis will take place after accrual of approximately 939 MACE events. For the primary non-inferiority analysis of MACE, the two-sided adjusted CI for the HR will be calculated using an O'Brien-Fleming spending function to preserve the overall Type I error rate of 2.5% with respect to the non-inferiority margin of 1.3. The analysis at approximately 714 MACE events corresponds to an information fraction of approximately 76%, and the amount of alpha to be spent for this analysis is about 1.0% (one-sided). The subsequent secondary hypothesis tests will utilize a similar O'Brien-Fleming alpha spending approach with a 2.0% two-sided alpha spend for each hypothesis at the interim. If at the end of the study, the upper bound of the two-sided adjusted CI is <1.3 for MACE, the study will be considered to have met its primary objective of demonstrating the non-inferiority of ertugliflozin as compared to placebo with respect to cardiovascular safety. Details regarding alpha spending and power for the primary analyses at each potential analysis time are described in Table 6 below.

Table 6. Alpha Adjusted Confidence Interval and Power for Primary Analyses

Stage	Analysis (within Stage)	Events (confirmed by adjudication)	Alpha for adjusted confidence interval (one-sided)	Power to Demonstrate Non-Inferiority*
1 Phase 2 and 3 Meta-analysis	1 Interim	130 MACE plus	1.0%	79.5%
	If the upper bound at interim analysis is ≥ 1.8 for MACE plus			
	2 Final	173 MACE plus	2.2%	95.1% (cumulative)
Once the 1.8 threshold has been met, the study will continue to Stage 2				
2 Study P004/B1521021	1 Interim	714 MACE	1.0%	83.8%
	If the upper bound at interim analysis is ≥ 1.3 for MACE			
	2 Final	939 MACE	2.2%	96.4% (cumulative)

* Power under HR=1.0

090177e187d04317\Approved\Approved On: 14-Mar-2016 14:12

Interim Futility Analysis for Secondary Endpoints

Furthermore, if non-inferiority on MACE (1.3 margin) is achieved at the Stage 2 interim analysis, but superiority on cardiovascular death or heart failure hospitalization is not achieved at that same analysis, the conditional power for achieving superiority at the subsequently planned analysis will be computed by an appropriately firewalled cardiovascular analysis team and provided to the E-DMC for assessment as described in the Data Access Plan. Depending on the results of this conditional power evaluation, the study may be continued in order to use the remaining alpha to conduct further superiority testing of the secondary endpoints. Under such a scenario, the study could be continued up to the pre-specified maximum number of events (ie, approximately 582 composite events of cardiovascular death or heart failure hospitalization and approximately 377 events of cardiovascular death). On the other hand, if the conditional power for superiority is not high enough, the study may be terminated having achieved the primary objective of demonstrating non-inferiority for MACE in Stage 2. The relevant decision criteria for assessing the conditional power for superiority will be included in the Statistical Analysis Plan. The assessment of conditional power for superiority will be considered as a non-binding futility assessment for the secondary endpoints.

Stage 2 Type I Error Rate Control

The overall Type I error rate in Stage 2 will be strongly controlled using a combination of fixed sequential testing across endpoints and alpha spending approaches across analysis time points.^{17,18} The following chart summarizes the alpha levels that will be utilized for each endpoint at each analysis time point in Stage 2. The fixed sequential testing sequence of the endpoints is described in [Section 9.3](#). Note that alpha allocated to the secondary superiority tests at the interim will be considered to be consumed even if the test is not conducted due to the hierarchical testing sequence. Also note that if the primary non-inferiority test is successful at the interim, but the study continues to the final analysis for the secondary superiority tests, a supportive analysis of the primary non-inferiority hypothesis will be conducted at the final analysis time point using the full alpha level of 0.025. Similarly, if the secondary superiority test for the composite of CV death and hospitalization for heart failure is successful at the interim but the study continues to the final analysis (ie, the secondary superiority test for CV death is not successful at the interim), a supportive analysis of the secondary superiority hypothesis for CV death and hospitalization for heart failure will be conducted at the final analysis time point using the full alpha level of 0.05.

090177e187d04317\Approved\Approved On: 14-Mar-2016 14:12

Sequence Number*	Endpoint (test)	Alpha for adjusted confidence interval	
		Interim Analysis	Final Analysis
1	MACE (non-inferiority)	1% (one-sided)	2.2% (one-sided); if test not successful at interim
			2.5% (one-sided); if test successful at interim
2	Cardiovascular death/hospitalization for heart failure (superiority)	2% (two-sided)	4.4% (two-sided); if test not successful at interim
			5% (two-sided); if test successful at interim
3	CV death (superiority)	2% (two-sided)	4.4% (two-sided)
4	Renal composite (superiority)	2% (two-sided)	4.4% (two-sided)

*Note: If the result of the test at any step of the sequence is not statistically significant, then testing will stop so that tests further down in the sequence will not be conducted (and therefore not considered successful).

The various possible actions to be taken based on the Stage 2 interim analysis results are summarized in the following table:

Scenario at Interim	Action
Primary test unsuccessful	Study continues to final analysis
Primary test successful and CV death/hospitalization for heart failure composite endpoint unsuccessful but not futile	Study continues to final analysis
Primary test successful and CV death/ hospitalization for heart failure composite endpoint futile	Study may be stopped for success on the primary objective and futility on the secondary superiority objectives
Primary test and CV death/ hospitalization for heart failure composite both successful; CV death unsuccessful	Study continues to final analysis
Primary test, CV death/ hospitalization for heart failure composite, and CV death all successful	Study may be stopped for success (regardless of the outcome for the renal composite)

The interim analyses will be performed by an independent team of statistician(s) and programmer(s) and will be reviewed by the E-DMC to determine whether excess risk with ertugliflozin relative to the non-ertugliflozin comparator group or to placebo (HR>1.8 or 1.3) may be ruled out. The results of the meta-analysis (Stage 1) will be submitted to regulatory authorities. Only upon request from or with agreement of regulatory authorities may the three glyceamic sub-studies be analyzed and submitted while the main study is on-going.

9.8. Insulin with or without Metformin, SU Monotherapy Add-on and Metformin with SU Glycemic Sub-Study Analyses

Primary Efficacy Analyses: The primary analysis population for each sub-study will be the sub-study Full Analysis Set defined as all subjects randomized receiving those specific background treatments at baseline, who meet all sub-study inclusion criteria (eg, minimal

090177e187d04317Approved\Approved On: 14-Mar-2016 14:12

dose(s) and dose stable period), who have received at least one dose of investigational product and have at least one observation of HbA1c during the time of the sub-study, including baseline and post-baseline time points up to Week 18 inclusive. If subjects receive glycemic rescue therapy, the observations post rescue therapy will be excluded from efficacy analyses of the primary and secondary endpoints.

The primary endpoint of HbA1c will be analyzed using a constrained longitudinal data analysis (cLDA) model with the following fixed effects:

- Treatment (categorical);
- Visit (categorical);
- Treatment by visit interaction;
- Baseline eGFR;
- Metformin use (yes/no; applicable for insulin (with or without metformin) sub-study only).

This model assumes a common mean across treatment groups at baseline and a different mean for each treatment at each of the post-baseline time points. In this model, the response vector consists of baseline and the values observed at each post-baseline time point. Time is treated as a categorical variable so that no restriction is imposed on the trajectory of the means over time. No explicit imputation of missing assessments will be performed. The treatment difference in terms of mean change from baseline to the primary time point of Week 18 will be estimated and tested from this model using least-squares means and 95% confidence intervals. The two-sided p-value will also be provided for testing the significance of the difference between treatment groups. An unstructured covariance matrix will be used to model the correlation among repeated measurements. The Kenward-Roger adjustment will be used with restricted (or residual) maximum likelihood (REML) to make proper statistical inference. Sensitivity analyses will be planned to assess the robustness of the primary model. Descriptive and graphical summaries by treatment group and time point will also be presented.

The two primary hypotheses, comparisons of each ertugliflozin dose to placebo, will be tested sequentially to control the overall Type I error rate at 0.05. The 15 mg dose will be tested first, and the 5 mg dose will be tested if and only if a statistically significant result is achieved for 15 mg.

Secondary Efficacy Analyses: The proportion of subjects achieving an HbA1c <7% (53 mmol/mol) at Week 18 will be analyzed using a logistic regression model with terms for treatment (categorical), metformin use (yes/no; applicable for insulin with or without metformin sub-study only), Baseline eGFR, and Baseline HbA1c (continuous). Summary measures from the analysis will include the odds ratio, 95% confidence interval for the odds ratio, and p-value for the comparison of treatment groups.

090177e187d04317\Approved\Approved On: 14-Mar-2016 14:12

The secondary endpoints of fasting plasma glucose, body weight, and blood pressure will be analyzed separately by fitting constrained longitudinal data analysis models similar to that used for the primary endpoint. For the insulin with or without metformin sub-study, the change in insulin dose from Baseline to Week 18 will also be summarized.

Hypothesis testing in the insulin with or without metformin sub-study, the SU monotherapy sub-study and in the metformin with SU sub-study will be performed with a 2-sided alpha of 0.05. The Type I error rate will be controlled by following a fixed testing sequence. If the result of the test at any step of the sequence is not statistically significant, then testing will stop so that tests further down in the sequence will not be conducted, and the corresponding null hypotheses will not be rejected. All tests will be conducted at the 0.05 alpha level.

For each endpoint, there are two hypotheses: comparisons of each ertugliflozin dose to placebo. The 15 mg dose will be tested first, and the 5 mg dose will be tested if and only if a statistically significant result is achieved for 15 mg. Testing will advance to the next endpoint in the sequence if and only if a statistically significant result is obtained for both doses.

The endpoints will be tested in the following sequence:

1. Reduction of HbA1c from Baseline at Week 18.
2. Reduction of FPG from Baseline at Week 18.
3. Reduction of body weight from Baseline at Week 18.
4. Proportion of subjects achieving an HbA1c <7% (53 mmol/mol) at Week 18.
5. Reduction of systolic blood pressure from Baseline at Week 18.
6. Reduction of diastolic blood pressure from Baseline at Week 18.

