3.2. Insulin with or without Metformin Add-on Glycemic Sub-Study

This trial includes an 18-week sub-study to generate safety and efficacy data in T2DM subjects using insulin therapy alone or insulin with metformin as the only background anti-hyperglycemic treatment. The insulin with or without metformin sub-study has different requirements with respect to allowable background AHA than the main cardiovascular study.

Subjects are entered into the sub-study if they are using insulin ≥ 20 units/day (with or without metformin $\geq 1,500$ mg/day) as the only background anti-hyperglycemic treatment. Subjects can be on basal insulin alone (eg, insulin glargine, insulin detemir, Neutral Protamine Hagedorn (NPH) insulin, degludec), split mixed insulin (eg, 70/30) or basal insulin + prandial insulin (eg, regular, aspart, lispro or glulisine). Subjects receiving prandial insulin as their only insulin regimen, without basal insulin, are not eligible for enrollment into the sub-study. Insulin total daily dose variations of up to $\pm 10\%$ during the 8 weeks prior to the Screening visit (V1) or during the period between the Screening visit (V1) and randomization are permitted and fulfill the criterion of stable insulin therapy. It is recommended that the daily dose variations are compared to the average weekly dose to account for day-to-day variability. Further details on the inclusion criteria for the insulin with or without metformin sub-study can be found in [Section 4.1.1](#).

Subjects eligible for the main cardiovascular study using insulin with any diabetes regimen other than insulin with or without metformin $\geq 1,500$ mg/day or subjects not meeting the insulin type and dose requirements as specified in the inclusion criteria will be enrolled in the main study, but not in the sub-study. Further details on the exclusion criteria for the insulin with or without metformin sub-study can be found in [Section 4.2.1](#).

This insulin with or without metformin sub-study plans to enroll a minimum of 450 subjects who will be randomized in a 1:1:1 ratio to ertugliflozin 5 mg, ertugliflozin 15 mg or placebo. The sub-study randomization will be stratified by background therapy and geographic region. The background therapy stratification factor will have two levels: insulin alone and insulin

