4.3. Randomization Criteria

Subjects will be assigned a unique identifier via IVRS at the Screening visit (V1), which will be retained throughout the duration of participation in the trial. Subjects will be randomized into the trial at Day 1 visit (V2), provided that they have satisfied all subject eligibility criteria. Eligibility criteria are outlined in [Section 4.1](#), [Section 4.1.1](#) and [Section 4.1.2](#), and should be verified at the Screening visit (V1) and at the Day 1 visit (V2). A computer-generated randomization code using the method of random permuted blocks will be utilized to assign subjects to 1 of 3 treatment regimens (5 mg ertugliflozin once daily, 15 mg ertugliflozin once daily or matching placebo) on Day 1 visit (V2). For subjects enrolled under the original protocol, the randomization will be stratified by sub-study and by geographic region (within sub-study). The stratification factor for sub-study will have four levels: subjects entering the insulin with or without metformin sub-study on a background of

insulin alone, subjects entering the insulin with or without metformin sub-study on a background of insulin plus metformin, subjects entering the SU monotherapy sub-study and subjects entering the main cardiovascular study but not any of the aforementioned sub-studies. For subjects enrolled under Amendment 1, the randomization will be stratified by geographic region only.

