9. DATA ANALYSIS/STATISTICAL METHODS

Methodology for summary and statistical analyses of the data collected in this study are outlined here and further detailed in a statistical analysis plan, which will be dated and maintained by the sponsor. The statistical analysis plan may modify what is outlined in the protocol where appropriate; however, any major modifications of the endpoint definitions or their analyses will also be reflected in a protocol amendment.

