Assuming a standard deviation of 1.0% and a lost to follow up rate of 10%, a sample size of 450 subjects (150 per arm) will provide approximately 98% power to detect a difference of 0.5% in the reduction of HbA1c from Baseline to Week 18 between ertugliflozin and placebo using a 2-sided 0.05 alpha level test.

9.1.2. Sample Size for SU Monotherapy Add-on Glycemic Sub-Study:

The primary endpoint for the sub-study is the HbA1c change from Baseline to Week 18. It is estimated that approximately 170 subjects will be enrolled into the sub-study. The final determination of inclusion in the sub-study will be based on a programmatic assessment of the sub-study criteria.

Assuming a standard deviation of 1.0%, a lost to follow up rate of 10%, and a sample size of 170 subjects (~56 per arm), the power to detect a between treatment difference of 0.6% will be approximately 85% using a 2-sided alpha level of 0.05.

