9.1.3. Sample Size for Metformin with SU Add-on Glycemic Sub-Study

The primary endpoint for this sub-study is the HbA1c change from Baseline to Week 18. It is estimated that at least 260 subjects will satisfy the criteria for inclusion in this sub-study. Assuming a standard deviation of 1.0% and a lost to follow up rate of 10%, a sample size of 260 subjects (~86 per arm) will provide approximately 96% power to detect a difference of 0.6% in the reduction of HbA1c from Baseline to Week 18 between ertugliflozin and placebo using a 2-sided 0.05 alpha level test.

As there is no separate randomization stratum for the metformin with SU sub-study, this sub-study will consist of a sub-group of subjects from the “main cardiovascular study”

stratum. The determination of inclusion in the sub-study will be based on a programmatic assessment of the sub-study criteria; see [Section 3.4](#).

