9.2. Primary Cardiovascular Endpoints Analysis

The two doses of ertugliflozin will be pooled for the analysis of cardiovascular endpoints. The analyses described below will be performed at the interim analysis and at the end of the trial.

The Stage 1 meta-analysis population will include all randomized subjects who have taken at least one dose of investigational product across the Phase 2 and 3 development program. The Stage 2 non-inferiority analysis population will include all randomized subjects who have taken at least one dose of investigational product in this study. For both stages, subjects will be analyzed in the group to which they were assigned by IVRS, regardless of the actual treatment received and only events confirmed by the Endpoint Adjudication Committee will be included in the analysis. For Stage 1, all confirmed MACE plus events will be included in the primary analysis. For Stage 2, confirmed MACE events occurring between randomization and 365 days after the last dose of study treatment will be included in the primary non-inferiority analysis.

The MACE plus and MACE endpoints will be analyzed using a stratified Cox proportional hazards model including treatment group as a covariate. For the Stage 1 meta-analyses, the Cox model will include “Study” as a stratification factor with the following three levels: cardiovascular study, placebo-controlled non-cardiovascular studies, and active-controlled non-cardiovascular studies. For the Stage 2 analyses, the Cox model will include “Cohort” as the stratification factor with the following levels: Cohort 1 (subjects randomized between December 2013 and July 2015) and Cohort 2 (subjects randomized in 2016 and beyond). A test of non-inferiority at the one-sided 0.025 significance level will be performed based on the Cox model. The upper bound of the alpha-adjusted two-sided confidence interval (CI) for the hazard ratio (HR) (ertugliflozin to a non ertugliflozin comparator group or placebo) will be calculated using an O’Brien-Fleming alpha spending function and compared with the appropriate non-inferiority margin (1.8 or 1.3).

Kaplan-Meier curves for the distribution of time to MACE and MACE plus will also be provided for each of the three treatment groups.

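### Cheap improvement, low impact: the insulin and SU monotherapy sub-studies are randomised within geographic region, but the protocol's cLDA models for them leave region out

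*Protocol*

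**What the plan says.** Only subjects enrolled under the original protocol can enter a sub-study. Protocol Section 4.3 says of them: "For subjects enrolled under the original protocol, the randomization will be stratified by sub-study and by geographic region (within sub-study". SU monotherapy is one level of the sub-study factor, and the insulin sub-study takes two levels, split by metformin use. Section 3.2 repeats the scheme for insulin: "The sub-study randomization will be stratified by background therapy and geographic region".

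Section 9.8 lists the fixed effects of the HbA1c cLDA model: treatment, visit, their interaction, baseline eGFR and "Metformin use (yes/no; applicable for insulin (with or without metformin) sub-study only". Region is not listed. FPG, body weight and blood pressure get similar models. The logistic model for HbA1c below 7% also has no region term. Sensitivity analyses of the primary model are promised but not described.

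Two passages limit the point:
- Section 9.1.3 explains why the third sub-study differs: "As there is no separate randomization stratum for the metformin with SU sub-study".
- Section 9 says: "The statistical analysis plan may modify what is outlined in the protocol where appropriate". The SAP supplied is a supplement on heart failure analyses. The primary SAP it refers to is not among the documents.

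**The concern.** Balancing allocation on a prognostic factor removes that factor's contribution from the true variance of the treatment difference. A model that ignores the factor leaves the contribution in the residual variance. The reported standard error is then larger than the true one, so the test spends less than its 5% and gives up some power.

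The protocol gives no reason for keeping metformin use and leaving out region. SU monotherapy has the least room, at 85% planned power. HbA1c also comes first in the fixed sequence of Section 9.8, where a failed test stops everything after it.

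**Working it through.** **Inputs from the documents (Sections 9.1.1, 9.1.2 and 9.8).** SD 1.0, 10% lost to follow-up, two-sided alpha 0.05, 1:1:1 allocation. Insulin: 450 subjects, difference 0.5. SU monotherapy: 170 subjects, difference 0.6.

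**Assumed, because the documents give no figure.** Region explains a share R² of 2%, 5% or 10% of the residual variance of Week 18 HbA1c. The simulations also assume five regions of unequal size and permuted blocks of six.

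**1. Stated power.** Power = Φ(Δ/SE − 1.96), with SE = √(2/n).
- Insulin: n = 450 × 0.9/3 = 135, SE = 0.1217, Δ/SE = 4.108, power 98.4% (stated: about 98%).
- SU monotherapy: n = 170 × 0.9/3 = 51, SE = 0.1980, Δ/SE = 3.030, power 85.8%, or 85.1% with the noncentral t (stated: about 85%).

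Both figures reproduce.

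**2. Exact-balance limit.** Put k = √(1 − R²). With region omitted, the reported SE is unchanged but the true SE is k × SE.
- True alpha, region omitted: 2Φ(−1.96/k)
- Power, region omitted: Φ((Δ/SE − 1.96)/k)
- Power, region included: Φ(Δ/(k × SE) − 1.96)

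| R² | True alpha, omitted | SU power, omitted vs included | Insulin power, omitted vs included |
|---|---|---|---|
| 0 | 5.00% | 85.8 vs 85.8% | 98.4 vs 98.4% |
| 2% | 4.77% | 86.0 vs 86.5% | 98.5 vs 98.6% |
| 5% | 4.43% | 86.4 vs 87.5% | 98.6 vs 98.8% |
| 10% | 3.88% | 87.0 vs 89.1% | 98.8 vs 99.1% |

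**3. Imperfect balance.** Incomplete blocks weaken the balance, and so does the later check described in Sections 9.1.1 and 9.1.2: "The final determination of inclusion in the sub-study will be based on a programmatic assessment of the sub-study criteria". A simulation with Week 18 ANCOVA standing in for cLDA (1,500 designs per cell, Monte Carlo SE at most 0.04 points for alpha and 0.12 for power) gave, for R² of 2%, 5% and 10%:

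| | True alpha, region omitted | Power lost (points) |
|---|---|---|
| SU monotherapy | 4.8, 4.5, 4.0% | 0.4, 1.1, 2.4 |
| SU, 20% removed by the check | 4.8, 4.6, 4.2% | 0.1, 0.8, 2.1 |
| Insulin | 4.8, 4.5, 4.0% | 0.1, 0.2, 0.4 |

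If region explains nothing, adding it costs SU monotherapy 0.2 to 0.3 points.

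**4. Smaller SU enrolment.** Section 3.3 expects about 120 SU monotherapy subjects, not 170. With n = 120 × 0.9/3 = 36, the step 2 formulas give power of about 72% at R² = 0 and losses of 0.7, 1.7 and 3.4 points at the three R² values. The conclusion below uses the 170 on which the power statement rests.

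**5. Which terms are needed.** In a cLDA, baseline is part of the response vector, so a region main effect shifts baseline and Week 18 alike. Simulated SU type I error (10,000 trials per cell, REML, unstructured covariance, baseline and Week 18 only, Monte Carlo SE 0.2 points) was:

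| R² | No region | Main effect only | Main effect plus region-by-visit |
|---|---|---|---|
| 5% | 4.5% | 4.6% | 5.0% |
| 10% | 4.0% | 4.1% | 4.9% |

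The main effect alone recovers almost nothing.

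**The case against.** The best counter-argument is that there is no shortfall against plan. In the step 3 simulation, SU power without region is 84.9% to 85.7% at the three assumed R² values, against a stated figure of about 85%, and type I error is protected. That stands: this is an efficiency gain, and its size rests on an R² that the documents do not give. The improvement is also not free, because it costs SU monotherapy a little if region is not prognostic.

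The cLDA check has limits too. It used two time points, while HbA1c is measured at Day 1 and Weeks 6, 12 and 18. With five regions and four time points, the two region terms add 4 + 4 × 3 = 16 parameters, and that cost was not simulated. The insulin results come from ANCOVA with metformin use fully adjusted. In the cLDA, metformin use is listed as a main effect only and has the weakness shown in step 5.

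A reader might infer more in three places, and none is supported:
- **Logistic model.** Simulated SU type I error was about 4.0% to 4.2% without region and 4.7% to 5.0% with it. A similar gap appears when region has no effect at all: 4.4% vs 5.2% in one simulation (8,000 trials, Monte Carlo SE about 0.23 points) and 4.3% vs 4.8% in another. It looks largely like small-sample behaviour of the Wald test, so it is not evidence that omitting region causes it.
- **Stage 2 Cox models.** These use cohort "as the stratification factor with the following levels: Cohort 1 (subjects randomized between December 2013 and July 2015) and Cohort 2", although "For subjects enrolled under Amendment 1, the randomization will be stratified by geographic region only". Simulated with cohort alone vs cohort by region, rejection at HR 1.3 was 2.55% vs 2.53%, power was 95.95% vs 95.90%, and standard errors agreed to four decimals. The effect is negligible.
- **Metformin with SU.** It has no stratum of its own, and its simulated alpha stays near nominal (4.97%, 4.93%, 4.87%).

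**Conclusion.** The point holds for the insulin and SU monotherapy cLDA models as the protocol lists them, as a low-impact improvement. If region is prognostic beyond the model terms, those tests are slightly conservative: true alpha is about 4.8%, 4.4% or 3.9% at an assumed R² of 2%, 5% or 10% with exact balance, and somewhat closer to 5% with realistic balance. The power given up is about 0.4 to 2.4 points in SU monotherapy and at most 0.4 points in insulin. At R² = 0 nothing is lost.

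A reader might infer that the stated power or the type I error control is wrong. Neither is: the power figures reproduce, and the error is on the safe side. The primary SAP may already include region, so the finding concerns the protocol text only.

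**What to change.** First check the primary SAP. If it does not already adjust for region, then before each sub-study is unblinded add region and region-by-visit to the insulin and SU monotherapy cLDA models for HbA1c, and to the similar models for FPG, body weight and blood pressure. Pool small regions by a rule set on blinded data.

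Section 9.7 allows the sub-studies to be analysed during the main study at the request, or with the agreement, of regulators. If one has already been analysed, leave its primary result alone and report the region-adjusted model among the sensitivity analyses that Section 9.8 promises.

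Adding region to the logistic models is optional. If it is added, the pooling rule matters there, because at least one region had no responder in 22% to 38% of simulated SU trials with no drug effect. The Stage 2 Cox models need no change.

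The cost is low. Region is already recorded at randomisation, the SAP can carry the extra model terms, and no sample size changes. The price is 0.2 to 0.3 points of SU power if region turns out not to matter, plus the untested cost of the extra terms with all four HbA1c time points.
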